9.8.1. Description of comparator(s)

The comparator will be the diagnosis of hepatocellular carcinoma based on the typical features on contrast enhanced MRI or CT or histological diagnosis (biopsy or resection) or a consensus diagnosis of HCC as determined by the local MDT will be accepted as a diagnosis of HCC.

On study contrast enhanced MRI scans

For cases where a contrast enhanced MR is done following a positive surveillance test (on study ceMRI), lesions classified as LI-RADS 1 or 2 will be regarded as negative for HCC and lesions classified as LI-RADS 5 will be regarded as positive for HCC. Lesions classified as LI-RADS 3 or 4 will be regarded as indeterminate and will be followed up according to the local clinical routine. If LI-RADS 3 or 4 are designated as HCC by the local MDT, or they are proven to be HCC on biopsy, or they progress to LI-RADS 5 within the 30 months of follow-up then they will be defined as HCC for the analysis relating to the whole 30 month period of surveillance. In cases where LI-RADS 3 or 4 lesions remain under follow-up at the end of the 30 months follow-up without a clear classification as HCC or benign, or where they have been histologically proven to be benign, then they will be classified as negative for HCC for the purposes of the analysis. The classification of lesions at on-study ceMRI scans is shown below in Figure 2. The follow-up of LI-RADS 3 and 4 lesions in this situation will finish at the timepoint that visit 6 was due or at an earlier time point if a definitive classification is reached before then.

Figure 2: Flowchart for the classification of lesions detected on contrast enhanced MRI performed during the study following a positive surveillance test. In cases where lesions are determined as negative within the 30-month surveillance period, participants will re-enter the AMULET surveillance schedule until they complete the study. Where a positive for HCC diagnosis is made, participants will end their participation, will undergo no further surveillance and will be managed according to the recommendations of the local MDT. Participants with LI-RADS 3 or 4 lesions who are undergoing interval contrast enhanced imaging as recommended by the local MDT will be suspended from participation in AMULET.

End of Study contrast enhanced MRI scan

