9.11. Follow Up

Follow up visits/procedures after specific clinical outcomes (HCC diagnosis/liver transplant and death)

HCC Diagnosis

If a diagnosis of HCC is made during the study, no further in person follow up visits or nceMRI scans will take place. Follow up data will continue to be collected at 6 monthly intervals from hospital records.

Liver Transplant

If a participant receives a liver transplant during the study, no further in person follow up visits or nceMRI scans will take place. Follow up data will continue to be collected at 6 monthly intervals from hospital records.

Death

If a participant dies, the date and cause of death should be clearly documented using the 'Mortality' form within REDCap. In the event that a participant's death certificate is not available on hospital records, the local study team may be asked to contact the relevant GP to obtain date/cause of death data.

Long-Term Follow-up

The study teams will obtain data from NHS England, the NHS Central Register for Scotland and other patient registries on participants for up to 10 years after the last follow-up visit, phone call or email. This will be a passive follow-up with no participant involvement.

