11.2. Description of the Statistical Methods

Statistical analysis for Primary outcome measure

Measures of diagnostic performance will be determined per round of surveillance and over the 30 months of study participation.

Diagnostic performance per round of surveillance

At each round of surveillance, the following data will be calculated and compared between USS and nceMRI.

- 1. Number and proportions of positive surveillance USS and nceMRI see section 9 for definitions of positive tests
- Number and proportions of true positive (TP) and false positive (FP) USS and nceMRI. As each positive test will be followed by a full contrast enhanced MRI, TP and FP tests per round of surveillance will be calculated
- 3. Positive predictive value (PPV) of USS and nceMRI

Diagnostic performance for the overall study period of 30 months

For the purpose of this analysis, each USS and nceMRI scan for each participant completing the study will be assigned only one of the 4 possible diagnostic categories of: true positive (TP) or false positive (FP), true negative (TN) and false negative (FN). The sum of TP, FP, TN and FN in this analysis will therefore be equal to the total number of participants completing the study. TP and FP will be determined at each visit as described above. TN and FN will be determined at the end of the study when participants undergo the reference standard ceMRI as part of the study protocol. FN results will also include those cases that present with HCC during the study without a prior positive test (interval cancers) or cases where both USS and nceMRI are negative tests but a ceMRI scan is triggered by an AFP>20. Cases that are initially FP may subsequently change diagnostic category. For this analysis, the diagnostic category which is applicable at the end of the study will be used. For example, if a finding initially classed as an FP develops into an HCC that was correctly identified by the surveillance tests, then the diagnostic test will be counted as a TP for this analysis.

Sensitivity and specificity estimates will be calculated separately for nceMRI and USS and compared. Statistical significance of the observed differences in sensitivity/specificity will be evaluated using the McNemar's test of paired proportions, with a two-tailed P-value <0.05 used as the significance criteria.

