11.4. Analysis populations

All participants registered will be included in the analysis.

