11.7. The Level of Statistical Significance

Statistical significance will be set at p<0.05.

11.8. Procedure for Accounting for Missing, Unused, and Spurious Data.

Participants must attend the baseline and last visit (v6) and have at least one ceMRI (after a positive surveillance test, or as per protocol at the end of the study period) in order to be included in the final analysis. Participants who do not meet this will be removed and replaced for the purposes of the statistical analysis. All data from participants that fulfil this criterion will be used and analysed using intention to diagnose methods. This is to ensure that cases where a participant completes one surveillance test but not the other at a particular visit are still included. The diagnostic category of the missed test will be determined according to the diagnosis on that visit and the final diagnosis at the end of the study. In cases of HCC diagnosis, the missed test will be assigned as FN. In cases of FP results on the surveillance test performed at that visit, the missed test will also be assigned as FP.

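### Section 11.8 makes visit 6 a condition of entering the final analysis, but an HCC diagnosis ends all visits; applied literally it excludes every HCC diagnosed before visit 6 and contradicts 11.2, 11.4 and 9.13

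*Protocol*

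**What the plan says.** Section 11.8 sets the entry rule for the final analysis: "Participants must attend the baseline and last visit (v6) and have at least one ceMRI". A bracket says the ceMRI may follow a positive surveillance test or be the planned end-of-study scan. The next sentence reads: "Participants who do not meet this will be removed and replaced for the purposes of the statistical analysis".

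Two sections describe what happens at diagnosis. Section 9.8.1: "Where a positive for HCC diagnosis is made, participants will end their participation, will undergo no further surveillance". Section 9.11: "If a diagnosis of HCC is made during the study, no further in person follow up visits or nceMRI scans will take place".

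Section 11.2 describes the 30-month analysis. It says "TP and FP will be determined at each visit as described above", and it counts as false negatives both interval cancers and HCCs found only because AFP triggered a ceMRI. It also says "The sum of TP, FP, TN and FN in this analysis will therefore be equal to the total number of participants completing the study". Section 9.14 places a participant's end of study at month 30, visit 6.

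Section 11.4 defines the analysis population in one sentence: "All participants registered will be included in the analysis". Section 9.13 says that participants who withdraw are not replaced, because the sample size already allows for attrition.

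**The concern.** In 11.8 the visit-6 condition and the ceMRI condition are joined by an and. The bracket about a positive surveillance test qualifies only the ceMRI. A participant whose cancer is confirmed at visits 1 to 5 meets the ceMRI condition but has no further visits, so cannot meet the visit-6 condition. The same holds for interval cancers, for AFP-triggered diagnoses before visit 6, and for suspended LI-RADS 3 or 4 cases later classed as HCC before visit 6.

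These cases supply most of the true positives and paired false negatives behind the 30-month sensitivity, which is a primary outcome. If 11.8 governs, the McNemar comparison rests mainly on cancers diagnosed at visit 6. If 11.4 governs, they all count. The protocol does not say which prevails, so the population for a primary comparison is not fixed.

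**Working it through.** **1. The passages side by side**

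| Section | Effect on an HCC diagnosed before visit 6 |
|---|---|
| 9.8.1, 9.11 | No further visits, so no visit 6 |
| 11.8 | No visit 6, so removed and replaced |
| 11.2, TP and FN rules | Counted (TP at the visit, or FN if an interval cancer) |
| 11.2, completers sentence | Not counted, if completing means reaching visit 6 |
| 11.4 | Counted (all registered) |
| 9.13 | Withdrawals not replaced, against 11.8's replacement |

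**2. Reproducing the planned number of HCCs**

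Inputs from 11.3 and 11.2: McNemar's test, 90% power, two-sided 5%, nceMRI 80% and USS 50%. The correlation r between tests is not stated; r = 0.1 is inferred because it reproduces all nine sensitivity cells of Table 2.

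- Discordance ψ = p1(1−p2) + p2(1−p1) − 2r√(p1q1p2q2) = 0.40 + 0.10 − 0.04 = 0.46, with q = 1 − p for each test. The difference is d = 0.30.
- n = [1.960√ψ + 1.282√(ψ−d²)]² / d² = [1.329 + 0.780]² / 0.09 = 49.4, so 50. This matches Table 2 and the target of 50 HCCs.

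**3. Share of HCCs found at visits 1 to 5**

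Assumptions, none stated in the protocol: equal numbers of new HCCs in each of the five intervals; a pool already present at baseline worth 0, 1 or 2 intervals; Table 2's sensitivities taken as per-round values; rounds independent.

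At 80% and 50%, both tests are positive with probability 0.40 + 0.1√(0.16 × 0.25) = 0.42. Detection by either test is 0.80 + 0.50 − 0.42 = 0.88 per round.

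With a baseline pool of one interval, the numbers found at visits 1 to 5 are 0.880, 0.986, 0.998, 1.000 and 1.000. The total is 4.864 of 6, or 81%. The number left is 50 × 0.19 = 9.5.

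| Per-round detection by either test | Share lost (pool of 0 to 2 intervals) | Left of 50 |
|---|---|---|
| 77% (70% / 30%) | 74–81% | 9–13 |
| 88% (80% / 50%) | 77–84% | 8–11 |
| 94% (90% / 50%) | 79–85% | 8–11 |
| 40–50% (pessimistic) | 54–71% | 14–23 |

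**4. Power on what remains, 80% versus 50%**

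Power = Φ[(d√n − 1.960√ψ) / √(ψ−d²)].

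- n = 50: Φ[(2.121 − 1.329)/0.608] = 90%.
- n = 9.5: Φ[(0.925 − 1.329)/0.608] = 25%.
- n = 8: 22%. n = 11.4: 30%.

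**5. Simulation of the visit sequence**

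There are 50 HCCs, with 80% and 50% per-round detection and r = 0.1. Exit is at the first round with any positive test, and the rest are found by the visit-6 ceMRI. The test is the asymptotic McNemar.

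| Onset | HCCs left | Power on those left |
|---|---|---|
| Even over six rounds | 9.5 | about 26% |
| 30% present at baseline | 8.0 | about 19% |
| None present at baseline | 11.4 | about 32% |

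With even onset and all 50 HCCs kept, power is about 95%. It exceeds 90% because cancers missed in one round can be found in a later one. With an exact test in the same scenario, power falls from about 92% to about 8%. The estimated sensitivities move from 89% and 56% (all HCCs) to 80% and 50% (visit 6 only), which are simply the per-round inputs.

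**The case against.** The strongest reply is that the intention is plain. Section 11.2 determines true positives visit by visit and counts interval cancers. Section 11.4 includes everyone registered. Section 9.8.1 classes a lesion that progresses to HCC within 30 months as HCC for this analysis. Section 11.8 itself accepts a ceMRI after a positive test and assigns missed tests in cases of HCC. Section 11.1 says the SAP will be final before any analysis. On this view, one clause is badly drafted and an analyst would not follow it.

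Much of that stands. A reader might infer that the plan as a whole discards its early cancers, or that the power loss is what will happen. The documents do not support either: the loss follows only if the visit-6 clause is applied literally over 11.4. Nor is any single percentage lost a protocol figure; it depends on assumed onset and detection.

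A reader might also infer that the remaining cancers would over-represent those both tests had missed earlier and that are harder to see. The simulation does not test this, because it draws rounds independently and an earlier miss does not make a later one likelier.

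What does not stand is that the conflict settles itself. Section 11.8 is the only place with an operational inclusion rule, no sentence exempts HCC cases, and the completers sentence in 11.2 leans the same way. A SAP that follows 11.8 inherits the exclusion, and one that follows 11.4 contradicts 11.8.

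**Conclusion.** The contradiction is explicit and needs correcting before analysis. Applied literally, 11.8 excludes every HCC diagnosed before visit 6, against 11.2 and 11.4, and its replacement rule conflicts with 9.13.

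The size is conditional. With roughly even onset, a baseline pool of up to two intervals and the protocol's sensitivities used per round, about 74–85% of HCCs would be lost, leaving about 8–13 of 50. At 80% versus 50%, asymptotic McNemar power would be about 19–32% over the simulated onset patterns (8.0 to 11.4 HCCs left), and lower with an exact test, against the stated 90%. The protocol does not say which form of McNemar's test applies. Under pessimistic detection of 40–50% per round by either test, the loss is still 54–71%. In each case the 30-month sensitivity becomes close to a visit-6-only estimate.

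**What to change.** 1. **Section 11.8.** Replace the visit-6 clause. A participant with a baseline surveillance visit enters the 30-month analysis if either (a) HCC was diagnosed by any route accepted in 9.8.1 up to the time visit 6 was due, or (b) non-HCC status was assigned under 9.8.1 by then. State that (b) includes suspended LI-RADS 3 or 4 cases that 9.8.1 classes as negative without a visit 6. A rule requiring HCC-free status to be shown at visit 6 could drop these cases, which count as false positives, and so inflate specificity.
2. **Section 11.2.** Equate the sum of the four categories with the participants whose HCC status was determined, instead of those completing the study.
3. **Section 11.4.** Reconcile the all-registered statement with this population, for example by naming which analyses use which set.
4. **Sections 11.8 and 9.13.** Reconcile the two statements on replacement.

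The cost is a few sentences in the protocol and matching SAP wording. No new data are needed and no visit, scan or clinical procedure changes.

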11.9. Procedures for Reporting any Deviation(s) from the Original Statistical Plan

Any deviations from the statistical analysis plan will be described and justified in the final report.

11.10. Health Economics Analysis

No health economic analysis is planned. However, the data we collect on health-related quality of life will provide the building blocks for future health economic analyses.

12. DATA MANAGEMENT

The data management aspects of the study are summarised here with details fully described in the Data Management Plan.

12.1. Source Data

Source documents are where data are first recorded, and from which participants' CRF data are obtained. These include, but are not limited to, hospital records (from which medical history and previous and concurrent medication may be summarised into the CRF), clinical and office charts, laboratory and pharmacy records, diaries, microfiches, radiographs, and correspondence.

CRF entries will be considered source data if the CRF is the site of the original recording (e.g. there is no other written or electronic record of data). All documents will be stored safely in confidential conditions. On all study-specific documents, other than the signed consent, the participant will be referred to by the study participant number/code, not by name.

12.2. Access to Data

Direct access will be granted to authorised representatives from the Sponsor and host institution for monitoring and/or audit of the study to ensure compliance with regulations.

12.3. Data Recording and Record Keeping

Imaging data

Imaging data will be managed on the XNAT (www.xnat.org) imaging informatics platform, which is designed and set up specifically for studies of this kind. The central XNAT instance will be hosted by the University of Oxford. XNAT provides a web-based interface for uploading and sharing imaging data in a user-friendly and interactive manner. Recruiting sites will be able to use the web-based interface to upload their data. All images will be uploaded in DICOM format from MRI (nceMRI and contrast-enhanced MRI collected at end of follow-up or earlier if HCC detected) and USS scanners.

Imaging data anonymisation

Imaging data will be pseudonymised and labelled with the study ID at the site before being uploaded to the study XNAT.

If MRI data containing participant identifiable information (PII) are uploaded to the study XNAT, the XNAT allows for these PII to be stripped and the files to be labelled with the study ID in an automatic process.

USS data may contain PIIs in the images themselves although these will be acquired under study ID, so should be pseudonymised at the point of acquisition. In such instances a semi-automated process will be employed to remove / mask the PII before the files are stored.

This anonymisation process ensures that every effort will be made to ensure only pseudonymised data will be uploaded by the sites, and only imaging data labelled with the study ID are kept centrally for long term storage.

Data from questionnaires

Participants will complete paper versions of the EQ-5D-5L, HADS and patient experience questionnaires. Questionnaires will be labelled only with the study ID. Site personnel will then enter data from the questionnaires directly into the study REDCap CRF. The completed paper questionnaires will be stored securely at the sites.

Data from clinical notes

Data from clinical notes will be entered directly into the study REDCap CRF. The data extracted includes but is not limited to:

- 1. Basic demographics
- 2. Social history
- 3. Laboratory blood results
- 4. Liver disease aetiology
- 5. Cirrhosis diagnosis and severity
- 6. Medical history and medications
- 7. Imaging data
- 8. Feasibility end-points

12.4. Imaging data quality assurance process

All data stored in XNAT are associated with a user-defined project with users given access to data on a project-by-project basis, ensuring well-controlled data protection and security. XNAT enables quality control procedures and image analysis pipelines to be integrated and automated according to image type. QA of the nceMRI images will be performed on data upload, to provide feedback to the sites and resolve any significant issues before the next patient is scanned. QA will partly be based on automated analysis verifying compliance of acquisition parameters with prescribed protocol, and other meta-data in the DICOM header. In addition, simple quality metrics will be automatically extracted from the data (such as signal-to-noise ratio) and compared against benchmarks. If a problem is detected, the local physics contact and the central image acquisition lead will be alerted, and further analyses performed if needed to identify the source of the problem and implement a solution. A visual assessment by a trained image analyst will be performed to check for unexpected artefacts. For each participant, a report will be compiled summarising the results of the QA and returned to the recruiting site. We will implement a similar QA procedure for USS data.

12.5. Personal data

Participants' personal data will be collected and stored securely on the study REDCap database. If personal data are uploaded together with imaging data to the study online portals then these will be removed as soon as possible as described above. Electronic and physical documents containing personal identifiable information of participants such as the code-breaking file linking the study specific number with the study participant's identity/contact details will be produced and stored securely, centrally and at the recruiting sites. Informed consent forms and MRI safety screening forms containing participant's names will be stored securely in locked cupboards at study sites and access is only given to authorised study members and authorised personnel.

Personal data (such as contact details and information which could identify a participant) will be destroyed as soon as it is practical to do so and no later than 12 months after the end of the study. The personal identifiers contained in consent forms and MRI safety forms will be stored or accessed for up to 20 years after study end by the study sites, after which time the custodian will agree a date for destruction and it will be destroyed confidentially.

In order to facilitate long-term data collection of mortality and cancer related endpoints, study investigators may request patient information from NHS England, the NHS Central Register for Scotland and/or other patient registries. The minimum personally identifiable information will be recorded in REDCap for the purpose of linkage with patient registries. These may include NHS or CHI number, initials and date of birth of participants. Data returned to the research team will only contain the unique study specific number.

As part of our commitment to maximise patient/service user involvement in research, participants will give consent (optional) for their contact details to be retained to hear about future research projects. This will be kept securely and independently of the study records on the High Compliance Server, Oncology Department, University of Oxford and a copy of their consent will be filed with retained contact information in this case. This will allow investigators to contact participants about future ethically approved research.

12.6. Data storage and data sharing

Participant identifiable data will be held on the study REDCap database on University of Oxford secure servers. Participant identifiable data will not be shared with co-investigators outside Oxford.

Data labelled with the study ID (pseudonymised data) will be shared with co-investigators at the University of Nottingham, Bournemouth University, Glasgow Caledonian University, and Nottingham University Hospital NHS Foundation Trust, during the study.

Anonymised data may be shared with global academic, commercial or other collaborators after analysis and publication of results, which is expected to be after the end of the study.

Essential documents will be stored securely for 20 years and thereafter the custodian of the data will agree a date for destruction. During the retention period, essential electronic data will be archived on a secure server at the University of Oxford and essential paper documents will be stored in adequate, secure archiving facilities (please refer to section archiving)

